Treatment Follow-up Visits (Weeks 1-12). Table 3 illustrates the schedule of assessments for treatment follow-up visits. On Day 8 (week 1) participants will pick a day between 8 and 35 to be their target quit date considering that one goal of the study is to have participants take varenicline for several weeks before trying to quit to maximize effectiveness. In-person visits for study weeks 1, 3, and 5 will take approximately 30 minutes to complete as participants will have 30-minute ACT sessions, as described below. In-person visits for study weeks 2, 4, and 6 will take approximately 1 hour as participants will have ACT sessions, assessment of blood pressure and heart rate, and questionnaires to complete (see table 3). In-person visits for study weeks 8, 10, and 12 will take 30 minutes to complete as participants will not have ACT on these visits but will fill out questionnaires and have blood pressure/heart rate assessed. Telephone visits for study weeks 7, 9, and 11 will take ~35 minutes, as the last ACT sessions will be completed at these visits. Figure 3 illustrates the study design. In addition to the questionnaires given at baseline described above the following questionnaires will be given during the treatment phase: the **Client Satisfaction Questionnaire – 8** (CSQ-8; 39) is a standardized measure of treatment satisfaction that has been used widely across mental health services (40) and in smoking cessation research with varenicline preloading (18) and the **ACT Treatment Satisfaction Questionnaire (ACT-TSQ)** measures treatment satisfaction with ACT counseling using two force-choice response items and a Likert scale (9).

Brief description of ACT intervention: Previous work has demonstrated that ACT, delivered as either 10 in-person or 6 telephone-delivered sessions, was feasible as evidenced by very high rates of participant retention and satisfaction (9). Others have also found preliminary evidence for ACT facilitating abstinence when combined with NRT patches: 40% of bipolar smokers receiving face-to-face ACT therapy, and 33% of those receiving ACT telephone therapy, achieved 7-day PP abstinence. Notably, higher quit rates were observed in ACT-treated bipolar smokers compared with another cohort treated with mood management cognitive behavioral therapy (46). Further, there was face validity to the proposed mechanism of action of ACT with >50% of participants reporting increasing acceptance of cravings to smoke. When one considers that 7-day PPA rates at end of treatment in EAGLES bipolar smokers treated with NRT patch was 10.8%, and for SSD smokers was 15.2% (unpublished data), the potential 2 to 4-fold booster effects with ACT deserve further testing. The ACT treatment manual to be used in this pilot trial was developed by [name] and colleagues and was pilot tested in smokers with BD (9). The ten 30-minute sessions will target the six core processes in ACT: acceptance, cognitive diffusion, being present, self as context, defining valued directions, and committed action. The intervention relies heavily on experiential in-session exercises and metaphors as a means of helping smokers learn to apply ACT principles to the task of quitting smoking as well as managing negative affect. ACT counselors will have at least three years of counseling experience, established therapeutic skills (e.g., empathy), and a master's degree in clinical psychology. Counselors will receive 40 hours of didactic and role-play training in the ACT intervention provided by [name] prior to the study commencing. Counselors will be certified as study therapists prior to delivering ACT, defined as passing scores on fidelity measures as outlined in the ACT Adherence Raters' Manual (47). ACT treatment fidelity will be evaluated by [name] assessing a twenty percent random sample of each therapist's audiotaped calls. ACT sessions will be rated using the ACT Adherence Raters' Manual (47,48). [name] and the counselors will also meet biweekly to review implementation quality data and coordinate intervention delivery based on fidelity feedback he receives from [name].

Non-Treatment Follow-up Visits (weeks 13-24): Following discontinuation of the medication participants will be followed every 4 weeks until conclusion of the study assessing mood, any suicidal thinking, and nicotine or other drug use. Visits for study weeks 16 and 20 will be done via telephone and take approximately 30-45 minutes. The final visit at week 24 will take place at Pac-TAC and take approximately 1 hour to complete.

Medication Adherence: Although aware of their limitations, due to budgetary constraints we will use participant self-report and pill counts of capsules returned at the biweekly visits as the measure of study medication adherence. Compliance will be defined as having any (partial or full) daily dose of study drug for 80% of the planned treatment period of 84 days.

Medication Tolerability Outcome Measure - - We will also assess: 1) % participants in each dosing arm who tolerate twice daily dosing with no dosage reductions; 2) % participants in each arm who continue on treatment but with a dosage reduction to once daily dosing; 3) % participants who discontinue medication treatment, but continue in study (off treatment/in study; treatment discontinuation rate); and 4) % participants who discontinue treatment and study enrollment (e.g., study discontinuation rate).

Assessment of NPSAEs & 2° NPS safety outcome: We will use the identical procedures we helped develop and used in the EAGLES trial to monitor neuropsychiatric safety (7). Briefly, all NPS complaints that are volunteered, observed or solicited with the NAEI; any elevated scores on the mood-, sleep- and suicidality-related measures described above, and any proxy reports from collateral informants will be evaluated as potential NPSAEs by the study team. Each AE will be rated by one of the study clinicians as to its intensity using the standardized EAGLES procedure: Mild = no or minimal interference in functioning; Moderate = some interference in functioning; Severe = significant interference with functioning. Based on this scoring, we will determine the composite safety endpoint used in EAGLES (i.e., NPSAEs that were rated as moderate to severe across the 16 pre-specified domains). We will also examine the observed incidence of participants experiencing NPSAEs of any intensity (i.e., mild, moderate or severe) as our 2° NPS safety outcome during the 12-week active treatment phase plus 28 day as also done in EAGLES.

2° Efficacy Outcome: In keeping with the pilot nature of this trial, we will use 7-day point prevalence abstinence (PPA) at week 12 confirmed by expired CO levels ≥ 4 ppm and urine cotinine levels < 200 mg/ml as the secondary efficacy endpoint. We will continue to track smoking outcomes through week 24 using these same biochemical verification measures to assess 7-day PPA at week 24 as a tertiary outcome.

Other Secondary Outcome Measures: Our gathering of data on the MNWS, QSU-Brief, ISI, SEQ-12, Confidence to Quit Scale is exploratory in nature and is intended to provide preliminary information on the mechanism of action of combined varenicline and ACT in SMI smokers and their relation to NPSAEs. We will also explore ACT's effects on avoidance and inflexibility with the AIS at weeks 12 and 24.

Determination of the NMR: The ratio of trans-3'-hydroxycotinine (3HC) and cotinine (COT) will be measured in plasma using electrospray ionization liquid chromatography tandem mass spectrometry (ESI LC-MS/MS) technology adapted from the protocols described by Tanner et al. (45) and Lerman et al. (7). COT and 3HC in plasma will be determined by quantifying with standard deuterium labeled COT and 3HC, known as COT-d3 and 3HC-d3 (commercially available from Sigma-Aldrich). Plasma samples will be spiked with a known amount of COT-d3 and 3HC-d3, and samples will be subjected to MS to quantitate the endogenous levels of COT and 3HC by parallel reaction monitoring. LC-MS/MS will be performed on the high-resolution Orbitrap Q-Exactive LC -MS system located in the [name] lab in the Skaggs School of Pharmacy and Pharmaceutical Sciences. Standard plots of different amounts of deuterated and non-deuterated COT and 3HC standards into control plasma, followed by LC-MS/MS, will define the linear range of quantitative measurements, lower limit of detection, and reproducibility of replicate samples. Ratios of 3HC/COT will be calculated from quantitative MS data analyzed by the Skyline software. Reliability of these procedures in plasma is high with NMR measurements robust even to differences in analytic methods used by different laboratories (45). The NMR data will be compiled with the phenotypic data of this study to examine the relationship of NMR to NPSAEs and smoking cessation.

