9. RESEARCH DESIGN AND METHODS

Overview: This pilot trial is a Phase IV, 12-week, single center, randomized, double blind, parallel group comparison of low (0.5 mg twice daily with slower titration over one full week) versus standard dose (1.0 mg twice daily with standard titration) varenicline in SMI individuals with DSM-V BD or SSD with a 12-week, post-treatment follow-up (see Figure 3 for study design). The 16 visits after screening (Weeks 0-24) will take place using the guidelines developed by the UCSD Office of the Vice Chancellor for Research. Participants will be screened, randomized and follow the protocol according to the Research Ramp-Up phase under which the university is operating at that time of (i.e., orange, yellow, or green).

Full participation includes 14 treatment visits and 3 follow up visits. All in-person visits will take place at Pac-TARC. In addition to testing low dose varenicline in SMI smokers for the first time, three other innovative design features are incorporated to try to improve medication tolerability and short-term quit rates. 1) Plasma will be obtained at baseline to measure participants' NMR and to identify slow versus normal nicotine metabolisers. 2) A flexible quit date (between days 8-35) will be employed allowing varenicline preloading to occur prior to the TQD. 3) Ten sessions of ACT for smoking cessation will be delivered by trained counselors first in 7 in-person sessions followed by 3 sessions delivered via telephone to all participants. Randomization of participants will occur in a 1 (low dose) to 1 (standard dose) ratio and participants will be balanced on diagnosis (BD vs SSD), gender, race (White vs. non-White) and whether or not they are taking antiepileptic medications (e.g., carbamazepine) as mood stabilizers (20) which, like the demographic/ethnic factors (11,26) can influence CYP2A6 activity and affect the NMR. Volunteered, observed and solicited NPSAEs will be assessed using standardized procedures developed in EAGLES and our other prior work (4,27). However, going beyond EAGLES, we will also assess participants' tobacco withdrawal symptoms, urges to smoke, sleep disturbances, self-efficacy & confidence to quit, and satisfaction with the protocol elements. To further extend EAGLES, we will include more "real world" participants who are somewhat less psychiatrically stable and who have comorbid substance use disorders (SUDs) in early remission.

Figure 3. Study Design – ACTSLOW Pilot Trial

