To gather preliminary data on the NMR, the frequency distributions of the NMR values in this SMI sample will be compared with the published data from Lerman et al. (2015) in a large sample of NMI smokers that found a cutoff score of 0.31 as the demarcating point between slow (<0.31) and normal (including rapid) metabolisers. Based on this analysis, we will calculate Cohen's d effect sizes comparing slow metabolisers on standard dose vs. normal metabolisers on low dose, as well as standard deviations and CIs, for incidence of NPSAEs of any severity to examine the direction and magnitude of the effect. Secondary outcome measures will also be examined using the same methodologies including 7-day PPA at weeks 12 and 24, to guide future studies. Regarding the secondary efficacy outcomes, and anticipating possible quit-boosting effects from ACT and varenicline preloading, we predict 7-day PPA rates at week 12 will be at least comparable to those observed in varenicline-treated EAGLES SMI participants which was 28.2%, and that 7-day PPA rates at week 24 will be at least comparable to the 20.0% observed in EAGLES (unpublished data). To examine the possible confounding effect of variable lengths of abstinence depending on when participants first attempt to quit smoking within the quit window, we will examine the effect of a time factor (i.e., the number of days from the first dose of medication to the date of the first quit attempt) with the methodologies described above.

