Consistent with recommendations on the proper sizing for pilot studies literature (50,51,53), we chose a sample size of 60 participants based on maximal accrual expectations over a 15-month recruitment period and practical cost constraints to conduct a pilot trial in this special population of smokers. Previous studies examining target sample sizes for pilot studies have argued that as few as 12 participants per group is adequate to estimate standard deviations for a two-group study (54,55), while others have suggested that a total sample of 30 is an acceptable size for a pilot study (56). With a sample of 60 (n=30 per dosing group), we will have the ability to estimate effect sizes, standard deviations, and their CIs with adequate precision to evaluate the feasibility of study procedures and to subsequently conduct formal power analyses for future RCTs (57). As such, it is amply sized as a pilot trial. For example, given a small-to-medium estimated effect of $d=0.40$, we would have 80% confidence that the true effect fell between 0.064 and 0.733 with a pilot sample of N=60. For a smaller effect of $d=0.30$, this 80% CI becomes 0.005-0.672 providing adequate precision in detecting an effect (i.e., zero not in the CI) for use in power analyses for a larger RCT. Furthermore, applying Sims' and Lewis' (2012) calculations, the sample size of N=60 will allow us to estimate standard deviations around our feasibility estimates with a minimal inflation factor (e.g., 1.09 for one-sided 80% CIs) for use in future RCT power analyses.

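### The four factors used to balance randomisation appear in none of the planned effect sizes, and arm balance does not protect the non-randomised metaboliser contrast in Aim 2

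*Combined protocol and SAP*

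**What the plan says.** Section 9, Overview, sets allocation to the two dose arms at 1:1 and then lists four balancing factors: "participants will be balanced on diagnosis (BD vs SSD), gender, race (White vs. non-White) and whether or not they are taking antiepileptic medications". The method of balancing (strata, blocks or minimisation) is not stated. The reason given is that antiepileptics, "like the demographic/ethnic factors (11,26) can influence CYP2A6 activity and affect the NMR". Diagnosis is a balancing factor but is not named there as affecting the NMR.

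Section 9, Data Analytic Plan, Aim 1: no formal testing. Cohen's d or odds ratios, with standard deviations and confidence intervals, are planned for the feasibility variables.

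Aim 2: Cohen's d compares slow metabolisers on standard dose with normal metabolisers on low dose for NPSAEs of any severity. "Secondary outcome measures will also be examined using the same methodologies including 7-day PPA at weeks 12 and 24". The only further factor to be examined as a possible confounder is the time from first dose to first quit attempt.

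Sample Size Determination: "With a sample of 60 (n=30 per dosing group") is said to give adequate precision for effect sizes, and at d = 0.40 "we would have 80% confidence that the true effect fell between 0.064 and 0.733 with a pilot sample of N=60".

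None of these places uses diagnosis, gender, race or antiepileptic use as a covariate or stratum.

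**The concern.** Two consequences follow, and they differ in kind.

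*Dose arms.* When allocation is balanced on a prognostic factor, that factor can no longer move the difference between arms, but an unadjusted standard error still counts its variance. For means and risk differences the interval then errs on the conservative side. The plan wants these effect sizes and intervals as inputs to power calculations for a larger trial, so their width matters somewhat.

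*Aim 2.* Participants are randomised to dose, not to metaboliser group, and the contrast takes one metaboliser group from each arm. Balance between whole arms does not carry over to these subsets. The plan itself says antiepileptics and demographic factors move the NMR. Its background section shows that diagnosis goes with NPSAE risk: the excess of moderate-to-severe events over smokers without mental illness is 7.73 points in bipolar disorder (BD) and 3.96 in schizophrenia spectrum disorder (SSD). Since antiepileptics are described as mood stabilisers, a link between their use and a bipolar diagnosis is plausible. A difference read as an effect of nicotine clearance could partly reflect these factors, and the plan includes no look at them.

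**Working it through.** **1. The plan's own figure.** Inputs from Sample Size Determination: 30 per arm, d = 0.40, two-sided 80%. The exact noncentral-t interval for a plain two-group d (58 df) is 0.0640 to 0.7326, which matches the stated 0.064 to 0.733. The planned precision is therefore unadjusted, with half-width (0.7326 − 0.0640)/2 = 0.334. (Separately, the stated interval for d = 0.30, "this 80% CI becomes 0.005-0.672", does not reproduce. The same method gives −0.034 to 0.632, which includes zero; the stated limits are those for d = 0.34.)

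**2. Dose arms, continuous outcome.** R² is the share of outcome variance explained by the four factors. It is not in the documents, so it is ranged.
- Width ratio = √(1 − R²) × t(0.90, 54)/t(0.90, 58) = √(1 − R²) × 1.2974/1.2963
- True coverage of a nominal 80% unadjusted interval = 2Φ(1.2816/√(1 − R²)) − 1

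| R² (assumed) | Width ratio | Adjusted half-width | True coverage, unadjusted |
|---|---|---|---|
| 0 | 1.001 | 0.335 | 80.0% |
| 0.05 | 0.976 | 0.326 | 81.1% |
| 0.10 | 0.949 | 0.317 | 82.3% |
| 0.20 | 0.895 | 0.299 | 84.8% |

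This presumes that balance is achieved on all four factors.

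**3. Dose arms, NPSAEs as a risk difference.** The only documented link is with diagnosis. The any-severity rate in varenicline-treated BD smokers is 45.3% (Table 1). The SSD rate is not given and is assumed to be 20–35%. With equal diagnosis groups, R² = [(p₁ − p₂)²/4]/[p̄(1 − p̄)].
- 45.3% vs 35%: (0.103²/4)/(0.4015 × 0.5985) = 0.011; gain 1 − √0.989 = 0.6%
- 45.3% vs 20%: (0.253²/4)/(0.3265 × 0.6735) = 0.073; gain 1 − √0.927 = 3.7%
- 45% vs 25% (assumed): 0.01/0.2275 = 0.044; gain 1 − √0.956 = 2.2%

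For the last case, trials were simulated with 15 people per arm-by-diagnosis cell. The actual SD of the risk difference was about 0.120 and the mean unadjusted SE 0.121. A stratified SE using the plug-in p(1 − p)/n averaged 0.116, which is too small. Its apparent 4% gain (ratio 0.960) falls to 2.3% (ratio 0.977) with an unbiased cell variance. The unadjusted nominal 80% Wald interval covered 78.6%.

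**4. Dose arms, odds ratios.** In simulations with minimisation on four binary factors and none, moderate or strong factor effects, the adjusted-to-unadjusted SE ratio for the log odds ratio was 1.05, 1.07 and 1.13. Conditional odds ratios become less precise on adjustment. For the risk difference the ratios were 1.00, 0.99 and 0.94.

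**5. Aim 2 contrast.** The background gives about 40% slow metabolisers among smokers without mental illness. Assuming that this carries over, the groups are 0.40 × 30 = 12 (slow, standard dose) and 0.60 × 30 = 18 (normal, low dose).
- At d = 0.40 the 80% interval is −0.086 to 0.879.
- With 15 BD participants per arm, the BD share in the two groups differs by chance with SE √[(0.25/12)(18/29) + (0.25/18)(12/29)] = 0.137, about 14 points.
- If the BD share differed by 20 points (assumption), diagnosis alone would create a difference of 0.20 × 10.3 to 0.20 × 25.3, or about 2 to 5 points.
- Simulations with no true NMR or dose effect, under assumed antiepileptic and race links, gave a bias of −3.0 to +1.0 points (odds ratio 0.87 to 1.05).
- For comparison, assumed rates of 45.3% vs 30% in 12 vs 18 give an odds ratio of 1.93 with 80% interval 0.72 to 5.22.
- Expected events are 12 × 0.453 + 18 × 0.30 = 10.8. Four covariates plus the contrast would leave about 2 events per coefficient.

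**The case against.** The strongest reply is that this is a pilot. Formal testing is not planned, clinical outcomes are declared secondary and unpowered, and the Aim 1 effect sizes are for feasibility variables judged against benchmarks, where the balancing factors hardly matter. A dose-arm effect size for clinical outcomes is implied by the precision statement but not spelled out. Any error is on the cautious side, and unadjusted SDs are a legitimate planning input. All of this stands and limits the weight of the point, but it does not explain why quit timing is examined as a confounder in Aim 2 while factors the protocol says move the NMR are not.

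Three stronger readings might be inferred, and the documents do not support them.
- *That dose-arm intervals for NPSAEs and abstinence are materially too wide.* In the binary case checked, the unadjusted SE is about right and its coverage is slightly below nominal. Coverage near 85% with 10% narrowing needs an R² of 0.20 on a continuous scale, which nothing in the documents supports.
- *That all four factors affect the NMR.* The text "can influence CYP2A6 activity and affect the NMR" refers to antiepileptics and demographic or ethnic factors. Diagnosis enters through NPSAE risk and, plausibly, antiepileptic use.
- *That the Aim 2 contrast is shown to be biased.* Confounding also requires an effect on the outcome. For NPSAEs the documents show this for diagnosis only, not for gender, race or antiepileptic use. Adjusting for a factor that acts only through CYP2A6 would cost precision and remove no bias.

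**Conclusion.** The point holds in limited form. The plan balances on four factors and uses none of them in its effect sizes. For continuous outcomes and risk differences, the dose-arm intervals are conservative if the factors are prognostic: by about 2%, 5% and 10% at R² of 0.05, 0.10 and 0.20, all assumed values. For NPSAEs by diagnosis the gain is about 1–4%, resting on an assumed SSD rate of 20–35%, and there is none for conditional odds ratios.

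The Aim 2 contrast is open to confounding because metaboliser group is not randomised. The illustrative size is a few percentage points, small beside the sampling error of about 12 vs 18 participants. Unlike sampling error, a systematic part would not shrink in a larger trial, and the data to examine it are already collected. The change is worth making because it is nearly free, not because the present results would be seriously wrong.

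**What to change.** **Dose arms.** State the balancing method. Report effects adjusted for the balancing factors beside the unadjusted ones: a linear model for scales, and a diagnosis-stratified or standardised risk difference for NPSAEs and 7-day abstinence. Use a variance suited to cells of about 15, since the plug-in form is too small. If a logistic model is fitted, report the standardised risk difference from it, because the conditional odds ratio does not narrow the interval.

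**Aim 2.** Tabulate all four factors, including diagnosis, by NMR-by-dose group. Add one sparse sensitivity estimate from all 60 participants with dose, NMR group, their interaction and, as first covariate, diagnosis; derive the planned contrast from it and label it exploratory. At the assumed 45.3% and 30% rates, 60 × (0.453 + 0.30)/2 gives about 23 events for four coefficients, which leaves little room for more. A four-covariate logistic model within the 30 contrast participants should not be attempted.

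**Cost.** A few degrees of freedom (width ratio 1.001 if the factors explain nothing), some SAP wording and no new data. The adjusted Aim 2 estimate will be imprecise and should be presented as such.
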